1.1 Study Objectives

PRIMARY OBJECTIVE

The primary objective of this study is to evaluate the overall performance of an investigational silicone hydrogel lens when compared to AOHP.

1.2 Study Description

Key components of the study are summarized in Table 1-1.

Table 1-1 Study Description Summary

Study Design – Part A	Prospective, randomized, parallel group, crossover, double-masked, bilateral, [REDACTED]
Study Design – Part B	Prospective, single group [REDACTED] single-masked, bilateral
Study Population	Volunteer subjects aged 18 or over who are habitual spherical weekly/monthly soft contact lens wearers, have at least 3 months of contact lens wearing experience, and who wear their habitual lenses at least 5 days per week and at least 10 hours per day. [REDACTED] [REDACTED] [REDACTED] [REDACTED] [REDACTED] [REDACTED] [REDACTED] [REDACTED]

	
Number of Subjects – Part A Target to complete: 60 (~30 per each parallel group) Planned to enroll: ~66
 
Number of Subjects – Part B Target to complete: 60 (~30 per each parallel group) Planned to enroll: ~66

Number of Sites	~4 US
Test Product	LID018869
Control Product	Control Product 1 (Part A): ACUVUE OASYS® with HYDRACLEAR® PLUS (AOHP) Control Product 2 (Part B): CooperVision® Biofinity® (Biofinity)
Planned Duration of Exposure – Part A	~60 days total duration (test and control): Test Product: ~30 days Control Product 1: ~30 days (2x ~15 days)
Planned Duration of Exposure – Part B	~30 days total duration (control only): Control Product 2: ~30 days
Visits – Part A	
Pre-Screening*
 
Visit 1: Screen/Baseline/Dispense Lens 1
 
Visit 2: Day 15 Follow-up Lens 1 [REDACTED]
 
Visit 3: Day 30 Follow-up Lens 1/Dispense Lens 2 [REDACTED]
 
[REDACTED]
 
Visit 4: Day 15 Follow-up Lens 2 [REDACTED]
 
Visit 5: Day 30 Follow-up Lens 2/Exit [REDACTED]
 
*Optional

Visits – Part B	
Pre-Screening*
 
Visit 1: Screen/Baseline/Dispense Lens 1
 
Visit 2: Day 15 Follow-up Lens 1 [REDACTED]
 
Visit 3: Day 30 Follow-up Lens 1/Exit [REDACTED]
 
*Optional

1.3 Randomization

[REDACTED]

Subjects for Part A of the study will be [REDACTED] [REDACTED] randomized in a 1:1 manner to receive treatment (lens) in a crossover sequence. No randomization will be implemented in Part B.

1.4 Masking

Part A of this study is double masked and Part B of the study is single masked (trial subject).

2 Analysis Sets

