1 PROTOCOL SYNOPSIS

Trial Sponsor	Alcon Research, LLC [name]
Name of Test Product(s)	LID018869
Name of Control Product(s)	Control Product 1 (Part A): ACUVUE OASYS® with HYDRACLEAR® PLUS (AOHP) Control Product 2 (Part B): CooperVision® Biofinity® (Biofinity)
Title of Trial	Clinical Comparison of Two Daily Wear Frequent Replacement Silicone Hydrogel Soft Contact Lenses
Protocol Number	CLY935-C020
Number of Sites	~4
Country	US
Planned Duration of Exposure – Part A	~60 days total duration (test and control): Test Product: ~30 days Control Product 1: ~ 30 days (2x ~15 days)
Planned Duration of Exposure – Part B	~30 days total duration (control only) Control Product 2: ~ 30 days
Number of Subjects – Part A	Target to complete: 60 (~30 per each parallel group)
	Planned to enroll: ~66
Number of Subjects – Part B	Target to complete: 60 (~ 30 per each parallel group)
	Planned to enroll: ~66
Study Population	Volunteer subjects aged 18 or over who are habitual spherical [REDACTED] soft contact lens wearers, have at least 3 months of contact lens wearing experience, and who wear their habitual lenses at least 5 days per week and at least 10 hours per day. [REDACTED] [REDACTED] [REDACTED] [REDACTED] [REDACTED] [REDACTED] [REDACTED]

	
[REDACTED]

Objective(s)	
The primary objective of this study is to evaluate the overall performance of an investigational silicone hydrogel lens when compared to AOHP.
 
[REDACTED]
 
[REDACTED]
 
[REDACTED]

Endpoints	
Primary Effectiveness
 
Distance VA (logMAR) with study lenses 
[REDACTED]
 
[REDACTED][REDACTED][REDACTED][REDACTED][REDACTED][REDACTED][REDACTED][REDACTED][REDACTED][REDACTED][REDACTED][REDACTED][REDACTED][REDACTED] 
Safety
 
AEsBiomicroscopy findingsDevice deficiencies
Assessments	
Effectiveness
 
Distance VA (logMAR) with study lensesDistance VA (Snellen) habitual correctionManifest refractionBCVA (Snellen distance with manifest refraction) 
[REDACTED]
 
[REDACTED]
 
[REDACTED]
 
[REDACTED]

	
 • [REDACTED] ■ [REDACTED] 
Safety
 
 • AEs • Biomicroscopy • Device deficiencies 	

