Study Design – Part A	 Prospective  Single group  Parallel group  Crossover  Other	 Single-masked (trial subject)  Single-masked (Investigator)  Double-masked  Open-label  Other
	 Contralateral  Bilateral  Monocular lens wear	 Randomized
	Randomization scheme [REDACTED] Sequence 1: LID018869 → AOHP Sequence 2: AOHP → LID018869	
Study Design – Part B	 Prospective  Single group [REDACTED]  Crossover  Other	 Single-masked (trial subject)  Single-masked (Investigator)  Double-masked  Open-label  Other
	 Contralateral  Bilateral  Monocular lens wear	 Randomized

	
contraindicates contact lens wear, as determined by the Investigator.
 
2. Any use of systemic or ocular medications for which contact lens wear could be contraindicated, as determined by the Investigator.
 
3. History of refractive surgery or plan to have refractive surgery during the study or irregular cornea in either eye.
 
■ [REDACTED]
 
■ [REDACTED]
 
■ [REDACTED]
 
6. Current or history of pathologically dry eye in either eye that, in the opinion of the Investigator, would preclude contact lens wear.
 
■ [REDACTED]
 
■ [REDACTED]
 
■ [REDACTED]
 
■ [REDACTED]
 
10. Wearing habitual contact lenses in an extended wear modality (routinely sleeping in lenses for at least 1 night per week) over the last 3 months prior to enrollment.
 
[REDACTED]
 
15. Current habitual wearers of AOHP.^e

--	---

	
[REDACTED]
 
[REDACTED]
 
[REDACTED]
 
[REDACTED]
 
[REDACTED]
 
17. Current habitual wearer of Biofinity family of contact lenses (comfilcon A).
 
■ [REDACTED]
 
[REDACTED]

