Associated Materials	
• CLEAR CARE® contact lens solution 
■ [REDACTED]
 
[REDACTED]
 
[REDACTED]
 
[REDACTED]
 
[REDACTED]

Table 1-1 Schedule of Study Procedures and Assessments – Part A

Procedure/ Assessment	PRESCREENING	LENS 1				LENS 2		USV
		Visit 1 Screen/ Baseline/ Dispense Lens 1	Visit 2 Day 15 Follow- up Lens 1	Visit 3 Day 30 Follow-up Lens 1 Dispense Lens 2		Visit 4 Day 15 Follow- up Lens 2	Visit 5 Day 30 Follow- up Lens 2 /Exit^	
				Follow-up Lens 1	Dispense Lens 2			
Informed Consent		X						
Demographics		X						
Medical History*		X	X	X	X	X	X	X
Concomitant Medications*		X	X	X	X	X	X	X
Inclusion/ Exclusion		X						
Habitual (lens brand, lens power*, lens care)		X						
VA w/ habitual correction* (OD, OS, Snellen distance)		X					X	(X)
Manifest Refraction and BCVA with manifest refraction* (OD, OS, Snellen distance)		X	(X)	(X)	(X)	(X)	(X)	(X)
Biomicroscopy		X	X	X		X	X	X
Randomization and record lens power*		X						
Dispense study lenses		X	(X) ^Ω		X	(X) ^Ω		(X)
VA w/ study lenses (OD, OS, logMAR distance)		X	X	X	X	X	X	(X)

Procedure/ Assessment	PRESCREENING	LENS 1			LENS 2			USV
		Visit 1 Screen/ Baseline/ Dispense Lens 1	Visit 2 Day 15 Follow- up Lens 1	Visit 3 Day 30 Follow-up Lens 1 Dispense Lens 2		Visit 4 Day 15 Follow- up Lens 2	Visit 5 Day 30 Follow- up Lens 2 /Exit^	
				Follow-up Lens 1	Dispense Lens 2			
[REDACTED]		■	■	■	■	■	■	■
[REDACTED]		■ ■	■ ■ ■	■ ■ ■	■ ■ ■	■ ■ ■	■ ■ ■	■
[REDACTED]			■	■		■	■	■
[REDACTED]		■ ■	■ ■ ■	■ ■ ■	■ ■ ■	■ ■ ■	■ ■ ■	■
[REDACTED]							■	■
[REDACTED]		■	■	■	■	■	■	■
[REDACTED]		■	■	■	■	■	■	■
AEs [§]		X	X	X	X	X	X	X
Device deficiencies		X	X	X	X	X	X	X
Exit Form		(X)	(X)	(X)	(X)	(X)	X	(X)

USV = Unscheduled visit

[REDACTED]

[REDACTED]

[REDACTED]

[REDACTED]

[REDACTED]

[REDACTED]

[REDACTED]

Table 1-2 Schedule of Study Procedures and Assessments – Part B

Procedure/ Assessment	PRESCREENING	Visit 1 Screen/ Baseline/ Dispense Lens 1	Visit 2	Visit 3 Day 30 Follow-up Lens 1/Exit^	USV
			Day 15 Follow- up Lens 1		
Informed Consent		X			
Demographics		X			
Medical History*		X	X	X	X
Concomitant Medications*		X	X	X	X
Inclusion/ Exclusion		X			
[REDACTED]		■			
Habitual (lens brand, lens power*, lens care)		X			
VA w/ habitual correction* (OD, OS, Snellen distance)		X		X	(X)
Manifest Refraction and BCVA with manifest refraction* (OD, OS, Snellen distance)		X	(X)	(X)	(X)
Biomicroscopy		X	X	X	X
[REDACTED]	■	■			
[REDACTED]		■	■	■	■
Record lens power*		X			

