3.3 Risks and Benefits

Contact lenses may offer improved peripheral vision and the convenience of not wearing spectacles. Material properties and design characteristics of the contact lens in development are features consistent with successful contact lens wear.

[REDACTED]

[REDACTED]

[REDACTED]

[REDACTED]

AOHP contact lenses are commercially available for daily wear use under a biweekly replacement schedule; Biofinity contact lenses are commercially available for daily wear use under a monthly replacement schedule; further details on any known potential risks and benefits can be found in the package insert. Refer to Appendix 13.1 and Appendix 13.2.

The site personnel will educate subjects on proper hygiene and lens handling, and compliance with the use of contact lenses according to the protocol. Subjects should be instructed not to wear contact lenses while sleeping or swimming. The site personnel will also advise the subjects to remove contact lenses and return for prompt follow-up of symptoms, such as ocular discomfort, foreign body sensation, excessive tearing, vision changes, or hyperemia.

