5.1.3 Visit 2 (Lens 1: Day 15 Follow-up) – [REDACTED]

1	Obtain information on any changes in medical health and/or the use of concomitant medications.
2	Record any device deficiencies or AEs, including those associated with changes in concomitant medication dosing, which are observed or reported since the previous visit. Collect any ADE/AE/Device Deficiency lenses [REDACTED]
■	[REDACTED]
■	[REDACTED]
5	Evaluate the study lenses by performing: VA with study lenses (logMAR OD and OS, at distance)
6	[REDACTED] 
■ [REDACTED]■ [REDACTED] [REDACTED] [REDACTED]

■	[REDACTED]
■	[REDACTED]
9	Perform slit-lamp biomicroscopy
10	If warranted, perform Manifest Refraction and BCVA with manifest refraction (OD, OS, Snellen distance)
11	Assess and record any AEs and device deficiencies reported or observed during the study visit. [REDACTED]
■	[REDACTED]
13	Schedule Visit 3 to take place 15 [REDACTED] days after Visit 2. [REDACTED]
■	[REDACTED]

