6.1 Subject Evaluability

The final subject evaluability for Part A will be determined prior to breaking the code for masked treatment (lens) sequence assignment and locking the respective subject data, based on the Deviations and Evaluability Plan (DEP).

Similarly, final subject evaluability for Part B will be determined prior to locking the database, based on the DEP.

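### Does a Day 15 replacement pair for AOHP alone undo the double-masking claimed for Part A?

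*SAP*

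**What the plan says.** SAP 1.4 is a single sentence: "Part A of this study is double masked and Part B of the study is single masked (trial subject". It names the masked party for Part B but not for Part A. The protocol synopsis ticks double-masked for Part A, and section 3.5 repeats the label; the words that follow it there are redacted.

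The exposure row of the synopsis reads "Test Product: ~30 days Control Product 1: ~ 30 days (2x ~15 days", and SAP Table 1-1 agrees. Protocol 3.3 adds: "AOHP contact lenses are commercially available for daily wear use under a biweekly replacement schedule". There are two sequences: "Sequence 1: LID018869 → AOHP Sequence 2: AOHP → LID018869".

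In the "Dispense study lenses" row of protocol Table 1-1, the marks at Visits 2 and 4 are conditional and carry the footnote sign Ω. The conditional mark at the Part A unscheduled visit does not carry it, nor does the one at Part B Visit 2 (Table 1-2). The footnote text is redacted.

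At Visit 2 (protocol 5.1.3), step 5 is "Evaluate the study lenses by performing: VA with study lenses (logMAR OD and OS, at distance" and step 9 is biomicroscopy; no lens-dispensing step is visible. Exclusion criterion 15 removes "Current habitual wearers of AOHP". Protocol 4.3 says that designated staff supply the lenses. Protocol 8.2 forbids disclosure of lens identity. Protocol 6.1 fixes evaluability "prior to breaking the code for masked treatment (lens) sequence assignment".

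**The concern.** The two lenses appear to be replaced on different timetables, and the difference falls on a study visit. A subject who gets a fresh pair at the midpoint of one period but not of the other has seen something that separates the lenses. With only two sequences, identifying Lens 1 also identifies Lens 2. The investigator works from a protocol that prints both the exposure row and the biweekly statement.

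This could matter because the primary endpoint, logMAR acuity, rests on the subject's own responses, and biomicroscopy is reported by severity grade (SAP 5.3.2). Expectation could influence either. With no formal test, the credibility of the Part A comparison depends largely on how the study is run. An unqualified double-masked label could then overstate the protection of the Day 30 and second-period data.

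**Working it through.** **1. Reproduce the plan's figure.** Test ~30 days plus AOHP 2 × ~15 days: 30 + 2 × 15 = 60 days, the stated Part A total. Four 15-day visit intervals also give 4 × 15 = 60. There is no alpha, power or sample-size calculation to reproduce.

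**2. Replacement pattern implied by the exposure row.**

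| Sequence | New pair at Visit 2 | New pair at Visit 4 |
|---|---|---|
| Test then AOHP | no | yes |
| AOHP then test | yes | no |

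The Visit 2 column alone separates the sequences. Suppose a fraction r of test wearers get an unplanned new pair at Visit 2 (an assumption; the documents give no rate). With 1:1 allocation, guessing AOHP whenever a pair is replaced is right with probability 0.5 × 1 + 0.5 × (1 − r). That is 1.00 at r = 0 and 0.90 at r = 0.20, against 0.50 by chance. This holds only for someone who sees the replacement and knows the schedules.

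**3. Readings taken after the possible cue.** Study-lens acuity is scheduled six times per subject: Visit 1, Visit 2, Visit 3 follow-up, Visit 3 dispense, Visit 4 and Visit 5. With 60 completers, 60 × 6 = 360. Follow-up biomicroscopy at Visits 2 to 5 gives 60 × 4 = 240. The counts below assume that dispensing comes after the Visit 2 and Visit 4 assessments.

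| Scenario | Acuity | Follow-up biomicroscopy |
|---|---|---|
| Replacement and its absence both inform | 60 × 4 = 240 of 360 (66.7%) | 60 × 3 = 180 of 240 (75%) |
| Only receiving a new pair informs | 30 × 4 + 30 × 1 = 150 of 360 (41.7%) | 30 × 3 + 30 × 1 = 120 of 240 (50%) |
| Concealed, unnoticed or not understood | 0 | 0 |

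The middle row is not a floor, because it already supposes that the cue is noticed and understood. Late dispensing is itself an assumption. It is plausible, since a Day 15 acuity check is most naturally made on the worn pair, and at Visit 4 a review-and-dispense row (item redacted) stands at step 12, after both assessments. If dispensing came before acuity at Visit 2, the top acuity count would be 60 × 5 = 300. None of these counts measures bias, which cannot be derived from the documents.

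**4. Would a less-cued comparison help?** The candidate is acuity at Visit 2 by lens, about 30 subjects against 30 others. Its standard error relative to the 60-subject within-subject comparison is √[(2/30) ÷ (2(1 − ρ)/60)] = √[2/(1 − ρ)], assuming equal standard deviations. The within-subject correlation ρ is not in the documents: ρ = 0.3 gives 1.69, 0.5 gives 2.00 and 0.8 gives 3.16. Lens age also differs at Day 30 (test ~30 days, second AOHP pair ~15 days), so a gap between the Day 15 and Day 30 results could not be put down to masking.

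**The case for a change.** The best case for acting does not depend on the redacted text. SAP 1.4 shows no redaction, and it specifies the masked party for Part B while leaving Part A open. The examiner has the protocol and therefore the schedules. Subjects habitually wear weekly or monthly lenses (SAP Table 1-1), so replacement interval is familiar to them; excluding current AOHP wearers limits brand recognition but does not stop anyone noticing a new pair. The remedies are cheap: a caveat, one summary of data already collected, and withholding the Visit 2 and Visit 4 dispensing fields from those who decide evaluability.

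The inference of a Day 15 pair for AOHP stands, and so does the brevity of SAP 1.4. The remedies fare less well:

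- A caveat that masking may be compromised would assert something the visible text does not establish. If protocol section 8 already covers the point, the caveat reduces to a cross-reference.
- The extra summary is less precise and does not isolate masking. By-visit summaries may already be planned, since the text after the descriptive statement in SAP 4.3.1 is redacted.
- Restricting dispensing fields presumes that the people deciding evaluability see them and that the Deviations and Evaluability Plan, which is not among the documents, does not already prevent it. Nothing visible supports either presumption.

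The visible safeguards also count. If the designated staff who supply lenses are not the examiners, the route to biased grading narrows or closes, although that alone would not protect the subject.

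**Conclusion.** No change follows. The exposure schedule creates a potential cue to lens identity from about Visit 2; whether it is an effective one cannot be judged from the public text. The affected acuity readings range from none to 240 of 360, and the affected follow-up biomicroscopy examinations from none to 180 of 240. Both ranges assume 30 completers per sequence and dispensing after the Visit 2 assessments. The reading that only AOHP is routinely replaced is itself inferred from the exposure row and the Ω marks.

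Little depends on the answer. The SAP declares success criteria not applicable, makes no inference on the primary endpoint and tests nothing for safety, and both documents call the study a descriptive pilot. No error rate, power or sample size moves. The difference in timetable comes from giving the two lenses different planned exposure patterns, and the place for concealment measures is protocol section 8, most of which is redacted. Naming the masked roles in SAP 1.4, with a pointer to that section, would be tidy but optional. The visible documents support neither an extra table nor a data-access rule.

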2.1 Safety Analysis Set

Safety analyses will be conducted using the safety analysis set on a treatment-emergent basis. As such, the safety analysis set will include all subjects/eyes exposed to any study lenses evaluated in this study. For treatment-emergent safety analyses, subjects/eyes will be categorized under the actual study lenses exposed in the corresponding lens sequence.

Adverse events occurring from the time of informed consent but prior to first exposure to study lenses will be summarized in subject listings.

3 Subject Characteristics and Study Conduct Summaries

The following tables will be presented for Part A [by lens Sequence or by Lens] and Part B separately:

- Subject Disposition [by Lens Sequence]
- Analysis Set [by Lens]
- Analysis Set [by Lens Sequence]
- Subject Accounting [by Lens Sequence]
- Demographics Characteristics [by Lens Sequence]

- Baseline Characteristics [by Lens Sequence] (habitual lens brand, habitual lens care brand, [REDACTED])

In addition, the following subject listings will be provided for Part A and Part B separately:

- Listing of Subjects Excluded from Protocol Defined Analysis Set
- Listing of Lens Sequence Assignment by Investigator
- Listing of Subjects Discontinued from Study

4 Effectiveness Analysis Strategy

This study defines one primary endpoint [REDACTED]. The Safety Analysis Set will be used for all effectiveness analyses.

Part A and Part B will be summarized and presented separately.

Continuous variables will be summarized using the number of observations, mean, standard deviation, median, minimum, and maximum. Categorical variables will be summarized with counts and percentages from each category.

All data obtained in evaluable subjects/eyes will be included in the analysis. No imputation for missing values will be carried out for the primary analysis.

A listing of select effectiveness data will also be provided.

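### Does the word *evaluable* in SAP 4 restrict the primary visual acuity summary to fewer subjects than the Safety Analysis Set?

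*SAP*

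**What the plan says.** **Analysis set.** SAP 4 (Effectiveness Analysis Strategy) states: "The Safety Analysis Set will be used for all effectiveness analyses". Protocol 6.4 says the same. SAP 2.1 and Protocol 6.2.1 define the set by exposure: "the safety analysis set will include all subjects/eyes exposed to any study lenses evaluated in this study". It is the only analysis set visible in SAP 2 or under Protocol 6.2.

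**Data handling.** Further down SAP 4, after the paragraphs on separate reporting of Parts A and B and on the choice of summary statistics, comes: "All data obtained in evaluable subjects/eyes will be included in the analysis". The next sentence, in the same paragraph, reads: "No imputation for missing values will be carried out for the primary analysis".

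**Evaluability.** Protocol 6.1 treats subject evaluability as a formal decision under the Deviations and Evaluability Plan (DEP). For Part A: "The final subject evaluability for Part A will be determined prior to breaking the code for masked treatment (lens) sequence assignment". For Part B it is settled before database lock. The readable SAP does not mention the DEP.

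**Use of the result.** SAP 4.2 and Protocol 6.4.1.1 make no inference on the primary endpoint. The SAP's executive summary says that success criteria do not apply. SAP 7 and Protocol 6.10 give no formal sample size calculation.

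**The concern.** *Evaluable* often has a technical meaning, and Protocol 6.1 appears to give it one: a status decided from protocol deviations, which is not the same as having worn a lens. SAP 4 could then be read as holding two inclusion rules, one by exposure and one by evaluability, with no statement of how they relate.

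An analyst holding the DEP decisions might drop exposed subjects from a VA table still labelled as the Safety Analysis Set. Another analyst would keep them. The two would report different numbers of observations and different means for the same lens. In a study whose whole primary result is a set of descriptive counts and means, the denominator is worth checking.

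**Working it through.** The plan has no power or sample size figure on this point to reproduce. The check is a comparison of the texts, followed by an illustration of size.

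**1. Which sentence sets the population?** The sentence on the Safety Analysis Set names a defined set and says that it covers all effectiveness analyses. Protocol 6.4 repeats it with no mention of evaluability. The later sentence names no set, cites no plan, says that data will be *included*, and does not say *only*. Taken literally it excludes nobody. Its neighbour is the no-imputation rule, so the paragraph deals with which values enter the summary: those observed.

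**2. Does *evaluable* in SAP 4 mean DEP status?** Protocol 6.1 speaks of subject evaluability and does not mention eyes. SAP 4 speaks of subjects/eyes, which is the unit used in the definition of the Safety Analysis Set. The link to the DEP is therefore an inference. A loose reference back to the defined set fits the wording at least as well.

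**3. How large could the effect be if the word were applied as a filter?** Let *f* be the fraction of exposed subjects left out and *d* the difference in mean VA between those left out and those kept.

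Mean of all exposed = (1 − *f*) × mean kept + *f* × (mean kept + *d*) = mean kept + *f* × *d*.

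The shift in one lens mean is therefore *f* × *d*. Planned enrolment of about 66 per part comes from the documents (SAP Table 1-1). The counts left out (1 to 6) and the gaps (0.05 to 0.20 logMAR) are assumptions, and so is taking all 66 as exposed.

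| Left out | Gap *d* | Shift *f* × *d* |
|---|---|---|
| 1 of 66 | 0.05 | 0.0008 |
| 3 of 66 | 0.10 | 0.0045 |
| 6 of 66 | 0.20 | 0.0182 |

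Leaving out both eyes of a subject gives the same fraction (12/132 = 6/66). If only 60 were exposed, the last row would be 6/60 × 0.20 = 0.020.

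**4. Effect on the comparison of lenses in Part A.** Subjects are "randomized in a 1:1 manner to receive treatment (lens) in a crossover sequence", so one who is left out after wearing both lenses leaves both means. The difference between lenses then moves by *f* × (*d*_test − *d*_AOHP):

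- equal gaps for both lenses: 0;
- both gaps within 0.05 to 0.20 in the same direction: at most 6/66 × (0.20 − 0.05) = 0.0136 logMAR.

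A subject who wore only one lens moves that lens's mean alone, so the bound in step 3 applies.

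**5. What would be visible?** SAP 4 reports the number of observations with every continuous summary. SAP 3 plans analysis set tables by lens and by sequence, and a listing of excluded subjects. A shortfall in the VA table against the analysis set table would therefore show.

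**The case for a change.** The strongest case for a change is that evaluability is formally decided and yet no visible analysis set uses it. SAP 4 is the only readable analysis text that seems to give it a role, so an analyst could reasonably look there for one. The no-imputation sentence already covers missing values, which leaves *evaluable* with no obvious job unless it is a filter. The outputs would not fully separate the two causes either. A smaller number of observations could come from missing data or from removal, and the exclusion listing refers to a set defined by exposure, so it need not show someone dropped from the VA table alone.

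Part of this stands. The word is undefined in the readable SAP, and the traceability limit is real. It does not show that the plan gives a wrong or uncertain result. A filter would have to override an explicit assignment that appears in both documents, on the strength of a sentence that excludes no one. The DEP is not among the documents. Protocol 6.6 (Handling of Missing Data), the natural counterpart of this paragraph, is listed in the contents but its text cannot be read. Either may settle the term, so the plan as a whole cannot be called silent.

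If evaluability were applied, the Part A decision would still be final before the sequence code is broken, so the choice of exclusions could not rest on the broken code.

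**Conclusion.** The concern does not hold as a defect. Followed as written, the plan summarises observed VA in exposed subjects and eyes, without imputation. That is a sound basis for a descriptive pilot comparison. *Evaluable* is a loose term that an analyst can resolve from the set assignment in SAP 4 and Protocol 6.4.

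Even on the less natural reading, the shift is about 0.001 to 0.018 logMAR in one lens mean. For subjects who wore both lenses, it is 0 to 0.014 logMAR in the difference between lenses. These figures rest on assumed counts and gaps, on all 66 enrolled being exposed and, for the difference, on gaps in the same direction; they are illustrative only. No test, power statement or success criterion would be affected. The conclusion also rests on the unseen Protocol 6.6 and DEP not directing that exposed subjects be removed from the effectiveness summaries; nothing readable suggests that they do. No change to the plan is called for.
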